2.0 Objectives and Purpose

Specific Aim #1. Determine if oral Oxandrolone administration will improve rotator cuff healing following rotator cuff repair.

Oxandrolone is an orally administered synthetic derivative of testosterone that is approved by the Federal Drug Administration (FDA) in patients who have lost weight resulting from extensive surgery, severe trauma, chronic infection, or as an adjunctive therapy to promote weight gain. It is also approved for bone pain associated with osteoporosis, and to attenuate protein catabolism associated with the prolonged use of corticosteroids. Oral administration of Oxandrolone has demonstrated increases in lean mass, protein synthesis, and wound healing with no long-term adverse events in trauma patients as well as healthy male controls.¹⁻³ The aforementioned safety and efficacy profile of oral Oxandrolone makes it an appealing adjuvant treatment to counteract the major biologic consequences of a chronically torn rotator cuff (muscle atrophy, fatty infiltration, and intercellular fibrosis), which are known to lead to poor healing and diminished clinical outcomes.^{4,5} The primary aim of this double-blind, randomized study is to compare the rotator cuff healing rates between an experimental group receiving 12 weeks of daily, orally administered Oxandrolone following rotator cuff repair to a control group undergoing the same rotator cuff repair and receiving 12 weeks of a daily, orally administered placebo medication. The healing spectrum from complete healing to re-tear will be defined based on a previously validated diagnostic imaging metric. The primary outcome measure is rotator cuff muscle-tendon structural healing as measured by the Sugaya classification on magnetic resonance imaging (MRI) at the primary end-point of 6 months.⁶ We will continue to follow for one year. We hypothesize that those in the experimental group (Oxandrolone group) will have greater rotator cuff tendon structural healing as compared to the control (Placebo group) at the primary end-point of 6 months post-operative.

The secondary measure of healing will be the degree of fatty infiltration of the muscle-tendon unit on MRI using the Goutallier grading classification.⁷ We hypothesize that those in the experimental group (Oxandrolone group) will have less fatty infiltrate as compared to the control (Placebo group) at primary end-point of 1 year.

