7.0 Clinical and Laboratory Evaluations

Program Time Line

Study participants will be tested on multiple occasions. Information will be collected prior to surgery, followed by measurements on the day of procedure, and 2, 6, 12, 24, 52, and 104 weeks after surgery. Surgery will be performed on an arranged date with the orthopaedic surgeon. Physical therapy will follow a pre-defined protocol with a physical therapist.

Testing Visits

Outcome measures and safety measures will be collected at routine postoperative visits with the operating surgeon. Dates and involved events are described in Table 1 below.

Schedule of Events

Event	Pre-Procedure	Procedure Day	Post-Operative Week					
			2	6	12	24	52	104
Informed Consent	x							
Demographics	x							
Confirm Inclusion/Exclusion Criteria	x	x						
Medical History	x	x						
Vital Signs	x	x	x	x	x	x	x	x
Randomization		x						
Blood draw: Testosterone level and Oxandrolone level	x		x			x		
Blood draw: Liver Enzymes	x		x			x	x	x
Outcomes:								
MRI: rotator cuff healing; Sugaya classification (primary outcome)	x				x		x	x
MRI: Fatty infiltrate (secondary outcome)	x				x		x	x
MRI: Muscle volume (secondary outcome)	x				x		x	x
Body Composition – lean mass & body fat (secondary outcome)	x		x	x	x	x	x	x
Questionnaires: ASES, VAS, PASS (secondary outcome)	x	x	x	x	x	x	x	x
Shoulder Range of Motion (secondary outcome)	x	x	x	x	x	x	x	x
Shoulder Strength (secondary outcome)	x	x	x	x	x	x	x	x

Table 1. Outline of pre- and postoperative timing of events and schedule of data collection.

Demographics.

Demographics of age, height, weight, race, arm dominance, and tear size and location will be recorded.

Inclusion and Exclusion Criteria.

The inclusion and exclusion criteria will be confirmed prior to enrolled, as described above in section 5.0.

Females of reproductive potential (women who have not been post-menopausal for at least 24 consecutive months, ie, who have had menses within the preceding 24 months, or women who have not undergone surgical sterilization, hysterectomy or bilateral salpingectomy or bilateral oophorectomy or tubal ligation) must have a negative serum or urine pregnancy test *with a sensitivity of ≤ 25 mIU/mL* within 48 hours prior to study entry.

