MRI – muscle volume (Secondary outcome). All participants will have a standardized MRI T2-weighted images without contrast, using the scapular plane of the sagittal-oblique image to measure supraspinatus muscle volume. Muscle volume will be measured by tracing the outer borders of the muscle, expressing the volume in mm^{2,34}.

Body Composition (Secondary outcome),

Study participants' lean mass and body fat percentage will be measured by bioelectrical impedance using Biospace InBody. The participant will have measurements at their preoperative visit and all postoperative visits.

Questionnaires (Secondary outcomes).

The participant will be asked to complete 3 questionnaires. Two questionnaires will be used to assess shoulder pain and function; American Shoulder and Elbow Surgeons Shoulder Assessment (ASES) to assess the patient-rated shoulder function on a scale of 0 -100 (0= no shoulder function/ disability), and a

Protocol Number: APP-17-01020

Version Date: 9/1/2017

Visual Analog Pain Scale (VAS) to assess the level of pain on a scale of 0 -10 (0 = no pain).¹¹⁻¹³ Patient satisfaction will be assessed with a single item question labeled the patient acceptable symptom state (PASS) questionnaire.^{11,14,15} The PASS is a 2-item question asking the patient their opinion of their current state of their shoulder, and if it is satisfactory for them. ASES, VAS, and PASS questionnaires at each visit to assess clinical outcomes.

Shoulder Range of Motion and Strength (Secondary outcomes).

Shoulder range of motion of flexion, abduction, external and internal rotation will be measured. During active range of motion, patients will be asked to move the shoulder as much as they can in the direction indicated by the investigator. Once participants reach their maximum range of motion, the measure will be recorded with a goniometer in degrees of motion. Two measures will be taken for each direction, and averaged for data analysis.

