8.0 Criteria for Evaluation and Endpoint Definitions

Outcome Measures

The primary outcome measure will be rotator cuff healing as measured by the MRI Sugaya classification.^{6,7} Measures will be performed at 12 weeks (the conclusion of Oxandrolone vs. placebo treatment), 6 months, 1 year and 2 years follow-up. The primary end-point will be 6 months.

Secondary outcome measures will include:

- 1) MRI evidence of rotator cuff fatty infiltration and muscle volume.
- 2) Patient-reported outcomes will be assessed with the ASES, a VAS, and PASS questionnaire.
- 3) Functional outcome will be assessed with shoulder range of motion with goniometer and isometric shoulder strength measures using a handheld dynamometer
- 4) Lean body mass and fat will be assessed with bioelectric impedance.

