10.0 Statistical Considerations

Statistical Methods

Descriptive statistics will be performed for participant demographics, historical information, intraoperative variables, as well as baseline testosterone, MRI measures of rotator cuff integrity, rotator cuff fatty infiltrate, rotator cuff muscle volume, shoulder strength, shoulder range of motion, patient-rated outcomes and body composition. Comparison for the primary outcome measure of rotator cuff integrity between groups from baseline to 1 year (primary endpoint) will be performed using a repeated measures analysis of Generalized Estimating Equation (GEE), appropriate for ordinal data. The GEE will also be used to compare between groups over time for the secondary outcome of fatty infiltrate (ordinal data). For all other secondary outcome variables, we will also use GEE for linear regression (ordinal data) or mixed model (continuous data) with repeatedly measured outcomes. Significance level will be established as $p < 0.05$. Analyses will be performed using STATA 13 software (College Station, TX) or SPSS and in consultation with the Statistics Department at USC.

Power Analysis and Sample Size

A power analysis for a sample size estimation was performed to detect a difference of 1 Sugaya grade (1-5 grades) classification (primary outcome) between the experimental and control group using 3 repeated measurements (baseline, 12 week, and 6 months).¹⁴ The power analysis was based with 2-sided alpha = 0.05 and power of 80%, and assuming a correlation among the repeated measures of 0.7 and overall SD of 2, giving a minimum sample size of 104 participants (n=52 participants in each group). This corresponds to an ANOVA effect size of 0.28 (28% of variance in primary outcome explained by treatment effect), or alternatively a moderate Cohen's D effect size (group mean difference divided by SD) of 0.5. Oversampling by 10% to account for possible attrition yields a total of 116 participants with 58 per group.

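### Body fat is measured only as a percentage, which a lean-mass gain lowers by itself, so a difference in it cannot be read as an effect on fat unless fat mass is also analysed

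*Combined protocol and SAP*

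**What the plan says.** The outcome appears in three places. Section 8.0, Outcome Measures, has "Lean body mass and fat will be assessed with bioelectric impedance". The Schedule of Events (Table 1, section 7.0) has "lean mass & body fat (secondary outcome". Neither gives a unit for fat. The Body Composition paragraph of section 7.0 is the only one that does: "lean mass and body fat percentage will be measured by bioelectrical impedance using Biospace InBody". Measurements are scheduled before surgery and at weeks 2, 6, 12, 24, 52 and 104.

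On the drug's expected effect, section 2.0 states, and section 4.0 repeats: "Oral administration of Oxandrolone has demonstrated increases in lean mass, protein synthesis, and wound healing".

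Section 10.0 does not name a body-composition response variable for the group comparison. It falls under the general sentence "For all other secondary outcome variables, we will also use GEE for linear regression (ordinal data) or mixed model (continuous data", at p < 0.05. No section mentions fat mass in kg, and none states a hypothesis or a time point for body fat.

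**The concern.** Body fat percentage is a ratio with lean mass in its denominator, and the plan expects the study drug to raise lean mass. A drug that adds lean tissue and leaves fat alone would show no difference in fat mass but a lower percentage in the oxandrolone arm. The percentage result would then partly restate the lean-mass result.

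What is at stake is interpretation. A difference in an outcome that section 8.0 simply calls fat could be taken as an effect on fat when it reflects lean mass only, and one drug effect could be counted as two body-composition findings. This follows from the definition of the ratio, so it holds even with a perfectly accurate device.

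**Working it through.** **Inputs.** From the documents: the fat metric is a percentage (section 7.0), the expected direction of the lean-mass effect is upward (sections 2.0 and 4.0), and the pre-attrition sample size is 52 per arm (section 10.0). Body weight W, baseline fat fraction f, lean gain g and the SD of change are not given, so the values below are assumptions. The plan states no figure for this outcome that could be reproduced.

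**Step 1: shift in the percentage with fat mass fixed.** Fat fraction = fat / (fat + lean). If lean rises by g and fat stays at W × f, the change in points is 100 × [W × f / (W + g) − f].

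For W = 85 kg, f = 0.30, g = 2 kg: fat mass is 25.5 kg before and after, and 25.5 / 87 = 29.31%, a change of −0.69 points. Other cases:

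| Assumed baseline | +1 kg lean | +2 kg | +3 kg | +4 kg |
|---|---|---|---|---|
| 85 kg, 30% fat | −0.35 | −0.69 | −1.02 | −1.35 |
| 70 kg, 35% fat | −0.49 | −0.97 | −1.44 | −1.89 |

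Over a wider range (70 to 100 kg, 20% to 40% fat, 1 to 5 kg gain) the fall runs from 0.20 points (100 kg, 20%, 1 kg) to 2.67 points (70 kg, 40%, 5 kg). The change in fat mass is 0 kg in every case.

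**Step 2: the fat loss that would look the same.** With lean mass held at 59.5 kg (85 − 25.5), a percentage of 29.31% corresponds to fat of 0.2931 × 59.5 / 0.7069 = 24.67 kg, a loss of 0.83 kg. Over the wider range the equivalent loss is about 0.25 to 3.1 kg. The percentage alone cannot distinguish the two explanations.

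**Step 3: recovering fat mass.** With lean mass L and fat fraction p from the same visit, fat mass = L × p / (1 − p). In the example, 61.5 × 0.2931 / 0.7069 = 25.5 kg, the unchanged value. This requires L to be all fat-free mass. If L leaves out a component B of fat-free mass, the formula returns fat × L / (L + B), which is too low. Multiplying the percentage by follow-up weight is not an assured alternative, because the plan lists weight only among the demographics, which Table 1 schedules before the procedure.

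**Step 4: how often the percentage would differ at p < 0.05.** For illustration, take a two-sample t test on change with 52 per arm. At SD 2 points the standard error is 2 × √(2/52) = 0.39, so the 2 kg example gives 0.69 / 0.39 ≈ 1.76 standard errors and a rejection probability of about 41%. For 70 kg and 35% fat it is about 69%. At SD 3 these become 21% and 37%. For 85 kg and 30% fat, a 1 kg gain at SD 3 gives about 9%, and a 3 kg gain at SD 2 gives about 73%. The spread shows how far the answer depends on the assumed inputs.

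**The case against.** The strongest reply is that section 7.0 simply defines what the shorter labels leave open. The protocol does the same elsewhere: section 8.0 lists range of motion and strength without units, and section 7.0 supplies degrees and kg of force. On that reading the outcome is body fat percentage throughout. This stands. A reader might infer two contradictory endpoints, but neither Table 1 nor section 8.0 says that fat means an amount.

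A reader might also set 41% or 69% against 5% and infer inflated type I error. The documents do not support that. In those scenarios the percentage truly differs between arms, so rejecting is correct for the endpoint as defined. The figures also rest wholly on assumed inputs and on a simple t test. The plan calls for a "mixed model (continuous data) with repeatedly measured outcomes", and three of the six postoperative visits (weeks 24, 52 and 104) fall after the 12 weeks of dosing.

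Finally, a reader might infer that the trial sets out to claim fat loss. It does not: none of the three aims contains a body-composition hypothesis, and the Feasibility part of section 3.0 groups body composition with the safety profile. Lean mass is also measured at the same visits, so an attentive reader could see a gain beside the falling percentage.

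What remains after all this is that nothing in the plan calls for fat mass to be derived or analysed, so the outcome labelled as fat is never examined separately from lean mass.

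**Conclusion.** The point holds as a minor one about interpretation. The labels are vague and section 7.0 resolves them to a percentage. Given the lean-mass gain that the plan itself expects, a between-arm difference in that percentage cannot by itself be read as an effect on fat. The direction is an identity and needs only the lean gain. The size, 0.20 to 2.67 points over the range examined, depends on assumed weight, fat fraction and gain, and any rejection probability depends also on an assumed SD. This is an unpowered secondary outcome with no stated hypothesis or time point.

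**What to change.** In Table 1, the Body Composition paragraph of section 7.0 and section 8.0, name the fat metric in the same words. In section 10.0, make fat mass in kg a response in the mixed model, alongside lean mass in kg. Keep body fat percentage as a supporting composition measure, and state that it will not be used to claim fat loss.

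Confirm from the device output that lean mass means all fat-free mass before relying on L × p / (1 − p), and settle the choice of metric before unblinding.

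The cost is a short wording change and one more derived variable, with no new visits, measurements or participants. The fat result may look less favourable than the percentage would.

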Shoulder strength will be measured using a hand-held device of: shoulder flexion, elevation on the scapular plane (scaption), external rotation, and internal rotation. The hand-held device (Hoggan Health Industries Inc., West Jordan, UT) is small device that contains a force transducer, measuring strength in kg of force. It is also commonly used in clinical settings, as it allows for accurate, and reliable measure. The arm of the patient will be positioned in a similar set of positions. The device will then be placed in contact with the distal segment. Participants will be asked to push against the device as hard as they can. Two measures for each movement will be collected. One-minute rest will be provided between measures.

Treatment

Orthopaedic Surgery

Rotator cuff repair will be performed by fellowship trained orthopaedic surgeons listed above.

Physical Therapy

Rehabilitation will follow a standard guideline under the supervision of a licensed physical therapist and the participant's physician.

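### Table 1 schedules maximal-effort strength tests two and six weeks after cuff repair, with no exemption or clearance rule, for values that no stated hypothesis needs

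*Combined protocol and SAP*

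**What the plan says.** Section 7.0 (Shoulder Range of Motion and Strength) sets out a single strength procedure. The arm is positioned, the device is placed against the distal segment, and "Participants will be asked to push against the device as hard as they can". The movements are flexion, scaption, external rotation and internal rotation; "Two measures for each movement will be collected", with a minute's rest between them. Section 8.0 describes the endpoint as "isometric shoulder strength measures using a handheld dynamometer".

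Table 1 (section 7.0) has eight time columns: pre-procedure, procedure day, and weeks 2, 6, 12, 24, 52 and 104. The strength row has eight marks, so every column is filled. Nothing states whether the procedure-day test comes before or after the operation.

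The oversight that the plan does describe is general. "Outcome measures and safety measures will be collected at routine postoperative visits with the operating surgeon". "Rehabilitation will follow a standard guideline under the supervision of a licensed physical therapist" and the participant's physician. Section 3.0 adds that the involved surgeons agree the rehabilitation protocol and that the treating surgeon is told of changes to the rehabilitation course. None of these provisions mentions the strength test.

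Section 2.0 sets the Aim 2 hypothesis on shoulder function at 1 year. Section 10.0 plans a mixed model on repeated measures for continuous secondary outcomes and names no early strength comparison.

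**The concern.** Taken literally, the schedule asks patients for all-out resisted effort two and six weeks after tendon repair. Section 1.0 says that incomplete healing and re-tear are common after this operation. The structure under test is also the one whose MRI integrity at 6 months is the primary endpoint. What is at stake is patient safety in both arms. The return is small, because the strength hypothesis is read at 1 year. If surgeons quietly decline to test at these visits, patients are spared, but the plan then produces missing values that it neither foresees nor records.

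**Working it through.** **1. Plan figure used.** The count below needs only the enrolment target. Section 10.0 gives 104 participants plus 10% for attrition: 104/0.9 = 115.6, rounded up to 116, or 58 per arm. This reproduces. The sample size rests on Sugaya grade, so changing the strength schedule does not affect it.

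**2. Exposure at weeks 2 and 6** (Table 1 and the section 7.0 procedure).
- Per visit: 4 movements × 2 measures = 8 maximal pushes.
- Per patient: 8 × 2 visits = 16.
- Whole trial: 16 × 116 = 1,856 at most, if everyone attends both visits.

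This counts efforts, not risk. Tear location varies and the documents do not map movements to tendons, so not every push need load the repair. If the procedure-day test were post-operative, it would add another 8 per patient.

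**3. Search for a safeguard.**
- Section 3.0, surgeon notification: covers changes to rehabilitation.
- Section 7.0, therapist and physician supervision: covers rehabilitation.
- Section 7.0, visits with the operating surgeon: gives no rule for withholding a test.
- Section 6.0, safety monitoring: covers liver enzymes, testosterone and oxandrolone levels, and drug reactions.

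None is a condition on the strength test.

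**4. What the 1-year contrast loses without weeks 2 and 6.** These values would enter the section 10.0 mixed model, so they are not unused. Assumptions: unit variance, 58 per arm, common baseline mean, free visit means, and all 10% attrition placed between weeks 6 and 12, which is the pattern least favourable to dropping the early visits. The procedure-day value is left out of both models. Let v1 be the week 52 variance given baseline, and v3 the variance given baseline, week 2 and week 6.
- With early visits: Var = (2/58) × [v3/0.9 + (v1 − v3)].
- Without: Var = (2/58) × [v1/0.9].

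| Assumed correlation | v1 | v3 | Bracket with | Bracket without | SE ratio |
|---|---|---|---|---|---|
| Exchangeable 0.7 | 0.51 | 1 − 3×0.49/2.4 = 0.3875 | 0.5531 | 0.5667 | 1.012 |
| Exchangeable 0.5 | 0.75 | 1 − 3×0.25/2 = 0.625 | 0.8194 | 0.8333 | 1.008 |
| 0.7 decaying per visit | 1 − 0.7^10 = 0.972 | 1 − 0.7^6 = 0.882 | 1.070 | 1.080 | 1.005 |

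In the first row the standard errors are 0.1381 and 0.1398. The 0.7 is borrowed from the section 10.0 Sugaya calculation; the plan gives no correlation for strength. With complete data both brackets equal v1 and the ratio is 1.000. If the 10% is instead lost after week 24, with exchangeable 0.7, the ratio is 1.003.

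**5. The procedure-day mark is a separate matter.** If that test is pre-operative, it is a second baseline value, and deleting it would cost precision even with complete data. With exchangeable 0.7, the week 52 variance is 0.51 given one baseline value and 1 − 2×0.49/1.7 = 0.4235 given two; √(0.51/0.4235) = 1.097. The 0% to 1.2% range covers weeks 2 and 6 only.

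**The case against.** The strongest reply is that the harm is not in the documents. Section 1.0 calls re-tear common but links none of it to strength testing, and two pushes per direction with rest are described only as a measurement. This stands as a limit: the hazard is a clinical inference. A reader might go further and infer that testing will damage repairs at some rate, bias the comparison, or cost the primary analysis power. The documents support none of that. They give no rate of test-related failure, both arms follow the same schedule, and any power figure would rest on an invented rate.

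A reader might also infer that patients are tested without supervision. That is not supported either. Outcomes are collected at visits with the operating surgeon, and the rehabilitation protocol, which is not reproduced, may well limit loading. What stands against the plan is that neither is tied to the test.

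Third, Table 1 may be a blanket template. It disagrees with the text elsewhere: section 6.0 puts liver enzymes at weeks 2, 6, 12 and 24, while the table marks weeks 2, 24, 52 and 104; and the table has no week 24 MRI although the primary endpoint is at 6 months. The early strength marks may therefore be unintended. That is a reason to correct them, since staff work from the schedule.

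Finally, week 12 is a judgment, and dropping the early visits leaves one post-operative strength measure in the 12-week dosing period. Both points are fair and are counted as costs.

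**Conclusion.** The point holds as a safety matter that should be fixed, with medium confidence. The plan schedules 16 maximal isometric efforts per patient over weeks 2 and 6, and leaves the timing of the procedure-day test open. It states no exemption, submaximal alternative or clearance condition. No stated hypothesis uses the early values, and losing them raises the week 52 standard error by 0% with complete data and by about 0.5% to 1.2% with 10% early attrition, under the assumed correlations. The conclusion rests on reading Table 1 literally and on the inference that maximal effort can stress a fresh repair. It makes no claim about the size of any risk, about bias or about power.

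**What to change.** - In Table 1, delete the strength marks at weeks 2 and 6.
- State that any procedure-day strength test is done before surgery only, or delete that mark. The first option is better if the value is to serve as a second baseline.
- Start post-operative strength testing at week 12, the next scheduled visit. The documents set no safe week, so the surgeons should confirm this choice.
- Allow the operating surgeon to withhold a test for safety. Record the reason and report withheld tests by arm, because they may depend on healing and leave missing values that are not random.
- Optional: maximal active motion ("patients will be asked to move the shoulder as much as they can in the direction indicated by the investigator") is marked at the same visits. It is unresisted and a lesser matter, but could be limited at weeks 2 and 6 to what the rehabilitation protocol allows.

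The cost is a table amendment and two or three sentences in section 7.0, with less work at two visits. The trial loses early strength values from the mixed model, keeps one post-operative strength measure (week 12) in the dosing period, and accepts the small loss of week 52 precision shown above. The sample size does not change.
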